L-theanine is the primary psychoactive component uniquely in green tea¹. Epidemiological studies support that green tea consumption is an independent factor associated with lower prevalence of depression²⁻⁴. Preclinical studies have demonstrated anti-depressant effect of L-theanine in rodents and provided evidences for its pharmacological properties of N-methyl-D-aspartate (NMDA) and gamma-aminobutyric acid (GABA) agonism⁵⁻ 7 . Yet these effects have not been proven in humans. Only one open-label clinical trial 8 has studied antidepressant effect of L-theanine in major depressive disorder, and suggested its effectiveness as an augmenting agent to an existing antidepressant regimen. Furthermore, the psychotropic properties and mechanism of L-theanine are to be elucidated. Paired-pulse transcranial magnetic stimulation (ppTMS) is a well-established technique to investigate frontal cortical excitability mediated by the inter-neuron NMDA and GABA receptors⁹. Several studies¹⁰⁻¹⁴ in subjects with MDD have demonstrated specific changes of ppTMS measures, including impaired short-term intracortical inhibition (SICI, mediated by GABA-A receptor and fast inhibitory postsynaptic potentials) and long-term intracortical inhibition (LICI, mediated by GABA-B receptor and slow inhibitory postsynaptic potentials) and intracortical facilitation (ICF, mediated by NMDA receptor and excitatory postsynaptic potentials), compared to healthy subjects. Treatment effects of MDD elicited by escitalopram corresponded with changes in these markers¹³. This is relevant to the study aim in that the motor cortex excitability is mediated by the glutamatergic system, and ppTMS offers an opportunity to investigate how L-theanine may manipulate the glutamatergic system in the frontal region by changing motor cortex excitability first in healthy subjects (phase 1, as described in this protocol). Then we plan to examine its potential as an augmenting agent for MDD in a placebo-controlled design (phase 2).

C. Experimental Method

C1. Brief Description of Subjects

Adults (N=10 completing all 3 visits) (>18 and <65 years old) without any neuropsychiatric disorders or contraindication to application of TMS will be recruited from the local community.

C2. Study Design

This is a double-blinded randomized order, cross-over, placebo-controlled trial to study the acute effects of a single dose of L-theanine on the motor cortex excitability, measured by paired-pulse TMS metrics.

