MOTOR THRESHOLD DETERMINATION: EMG will be recorded from the right abductor pollicus brevis (APB; thumb) muscle in order to measure the amplitude of motor evoked potentials (EMG) recorded by LabChart software throughout the procedure. The subject will be seated comfortably, given earplugs, and instructed to maintain relaxed throughout the experiment. Sticky electrodes will be attached to the skin around the thumb and wrist of the subject's right hand. Single pulses of TMS will be applied to the area of the left motor cortex corresponding with right thumb muscle ABP (using with a Magstim figure-of-eight magnetic coil and Magstim stimulators) to determine the resting motor threshold (RMT), defined as the intensity that produces a MEP in relaxed APB muscle of > 50 uV during 5 of 10 trials. This value is used to calibrate the intensity of pulses for the ppTMS measures of cortical excitability.

PAIRED-PULSE TMS PROTOCOL: Paired pulses of TMS will subsequently be used to assess various measures of cortical excitability. For example, for intercortical facilitation (ICF) measurement, a subthreshold conditioning stimulus (CS) at 80% RMT precedes a suprathreshold testing stimulus (TS) at 120%RMT. Inter-stimulus intervals (ISIs) of different durations, e.g., 10 ms and 20 ms will be used. ICI will be tested with a suprathreshold CS at 120% of RMT followed by test stimulus at 120% of RMT. Again, trials will be repeated with at ISIs of different durations, e.g. 2, 5, 50, and 100ms.

Each ppTMS protocol will consist of 25 trials for each of the six conditioned stimuli in random order. MEP amplitudes will be recorded from each trial. SICI, ICF and LICI metrics are estimated from averages of the conditioned MEP amplitudes.

DRUG ADMINISTRATION: The subject will be dispensed a single dose of either drug or placebo as prepared by an unblinded pharmacist. The subject will take placebo or L-theanine 400mg of with water and remain sitting in a quiet room for relaxation for 30min, after which the ppTMS protocol will be repeated. The PI/co-PI and the subject will be blinded to the result of randomization.

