SAFETY ASSESSMENTS: Prior to starting TMS procedures, the subject will be screened for TMS risk with a standard TMS Safety Screen questionnaire. Visual analog scales (e.g. sense of calm, anxiety level, sedation, irritability, level of fatigue), will be completed prior to and following each ppTMS protocol to evaluate effects of the stimulation as well as possible effects of L-theanine on mood. Verbal query will be used to elicit any other adverse effects. Subjects will be discharged from the research facility after each visit when it is clear they

are comfortable and suitable to drive home. The total estimated time for each visit is estimated to be 2.5 hours to 3 hours.

C4. Data Analysis

No previous studies have been done on the effects of L-theanine on intracortical facilitation or inhibition. However, many similar studies have been done with ppTMS to evaluate pharmacological effects of a drug on these same cortical excitability measures. Previous studies on the effects of NMDA receptor antagonists (dextromethorphan¹⁵, memantine¹⁶) on ICF and of GABA receptor agonist (benzodiazepine¹⁷) on ICI. Those studies had sample sizes that ranged from 8-10 healthy individuals. The estimated clinically meaningful effect size is 10% of change in the ICI and/or ICF. Thus, after consultation with [name] on sample size estimation, we plan to collect a full set of data from N=10 healthy subjects. The Pharmacy Department will participate in the process of L-theanine/placebo packing, storage, randomization and distribution.

SICI, ICF and LICI values were calculated by the ratio of conditioned MEP / unconditioned MEP. We used Wilcoxon signed-rank tests to compare the baseline-to-post-drug changes (Δ =post-drug value minus pre-drug value) of SICI, ICF and LICI between placebo and L-theanine conditions. Two-sided P value < 0.05 is considered statistically significant.

D. Material Inducements

Subjects will be compensated in the form of gift cards for their participation:

\$20 for participating in informed consent and initial SCID-5 interview;

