We plan to establish a data monitoring panel with the PI ([name]) and co-PI ([name]), and several unaffiliated clinical researchers with relevant expertise. The group will review the study and its progress prior to initiation. The PI/co-PI will present all adverse effect data to the panel and report any other issues related to safety. Weekly meetings between [name], [name] (and any BNRF staff involved in the project) will be held to review progress and adverse events.

We plan to do an interim analysis as mentioned above to re-estimate sample size, when N=5 subjects have been enrolled. In cases of any adverse effects from TMS or L-theanine, a comprehensive evaluation of the severity of the effect (and reported to the Butler IRB if determined a reportable event per IRB guidelines) and if

the subjects wish to stay in the study they will be aware they have the opportunity to withdraw at any time of the study. When statistically significant differences are observed for the ppTMS measures (SICI, LICI, ICF) in a dose-dependent correlation with L-theanine, or there are no differences observed whatsoever, the study will be concluded.

E. Potential Benefits

The study will contribute valuable data to elucidate the effects of L-theanine on motor cortex excitability. If the study yields positive results, it could support a phase 2 study on the effects of L-theanine on motor cortex excitability in patients with MDD and establish the foundation of L-theanine as a potential augmenting agent for pharmacotherapy of MDD.

F. Risk-Benefit Ratio

The risk-benefit ratio is estimated to be minimal considering the significant benefit that could be potentially generated from the study, versus the very low risks of the two procedures as mentioned above, as well as the measures that will be taken to further minimize those risks.

4) REFERENCES

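### D3's rule for concluding the study does not fit a single-dose, placebo-controlled design, and its absence-of-difference condition has no criterion and no stated look

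*Combined protocol and SAP*

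**What the plan says.** **The rule.** The second paragraph of section 3.D3 ends with a rule for ending the study on its ppTMS results. When significant differences in SICI, LICI and ICF appear "in a dose-dependent correlation with L-theanine, or there are no differences observed whatsoever, the study will be concluded". There are two conditions, joined by *or*.

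**The interim.** The same paragraph opens with a different plan: "We plan to do an interim analysis as mentioned above to re-estimate sample size, when N=5 subjects have been enrolled". Its stated purpose is sample size, and the conclusion sentence does not refer to it.

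**The design.** C2 describes a cross-over trial "to study the acute effects of a single dose of L-theanine on the motor cortex excitability". The drug administration text in C3 gives one active level: "The subject will take placebo or L-theanine 400mg of with water". Each subject receives active drug at one of visits 2 and 3 and placebo at the other.

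**The analysis and sample size.** C4 plans Wilcoxon signed-rank tests of the pre-to-post changes "of SICI, ICF and LICI between placebo and L-theanine conditions", with significance at two-sided P < 0.05. On sample size, C4 says "we plan to collect a full set of data from N=10 healthy subjects". C1 and 3.A also plan for 10 subjects who complete all three visits.

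**The concern.** A rule for ending a study should be one that the design can evaluate, and it should agree with the planned sample size. This one does neither.

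- The first condition asks for evidence that a trial with one active dose cannot produce.
- The second does not say what counts as no difference, whether one or all three measures must show it, or when it is assessed.
- A stop driven by the outcome data is therefore neither excluded nor defined, while three other sections plan for 10 completers.

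At stake is whether the plan fixes the end of the study independently of the results. With 10 planned subjects, ending a few early because nothing had yet reached significance would be a material departure. The interim in the same paragraph adds to the uncertainty, because it refers back to text that no earlier section contains and C4 gives no method for it.

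**Working it through.** The rule contains no figure to reproduce. The only related figure is N=10, and its derivation is not at issue here. The check is mainly logical, with one short calculation as illustration.

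**Inputs**
- Active dose levels: one, 400 mg once, plus placebo (Specific Aims, C2, C3; repeated in 3.C).
- Test: signed-rank, L-theanine against placebo, two-sided 0.05 (C4).
- Planned completers: 10 (C1, C4, 3.A).
- Only look named: five enrolled, for re-estimation (D3).
- Reported p-values: ICF 0.016, LICI 0.037, SICI 0.450 (section 8).

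**Step 1: the first condition.** The dose takes two values, 0 and 400 mg. Any correlation with dose over two points is just the drug-placebo contrast and says nothing about how the effect changes between active doses. No second dose, plasma level or weight-adjusted analysis is described. Dose-dependence therefore cannot be tested, whatever N is.

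**Step 2: possible outcomes set against the rule.**

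| Outcome | First condition | Second condition, literal | Second condition, read as nothing significant |
|---|---|---|---|
| At least one significant difference | Not met: no dose-dependence can be shown | Not met | Not met |
| Differences present, none significant | Not met | Not met | Met |
| Every difference exactly zero | Not met | Met | Met |

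The first row is the only positive result available, and no column covers it. The reported results fall in that row. The third row almost never occurs with ratios of MEP amplitudes, which are continuous. Under the literal reading the rule is almost never triggered. Under the other reading it can be triggered at any time, because no time is given.

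**Step 3: illustration at five pairs.** With n untied, non-zero pairs, the smallest exact two-sided signed-rank p is 2/2^n:
- n = 4: 2/16 = 0.125
- n = 5: 2/32 = 0.0625
- n = 6: 2/64 = 0.03125

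At five pairs the exact test cannot reach 0.05, and six is the smallest number at which it can. C4 does not say whether the exact or approximate test is used. For the normal approximation at n = 5, the mean is 5×6/4 = 7.5, the variance is 5×6×11/24 = 13.75 and the SD is 3.708. The most extreme result gives:
- without continuity correction: z = 7.5/3.708 = 2.02, p = 0.043
- with correction: z = 7.0/3.708 = 1.89, p = 0.059

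**Step 4: do the reported results suggest a stop at five?** The ICF p of 0.016 is below the five-pair minimum under all three versions (0.0625, 0.059, 0.043), so that analysis used more than five pairs. A rough n can also be recovered if Cohen's d is assumed to use the pooled SD of the two conditions. Then √n = (mean difference/d) / √((SE₁² + SE₂²)/2).
- ICF: (0.414/1.02)/0.1347 = 3.01, n about 9
- LICI: (0.213/0.91)/0.0800 = 2.92, n about 8.6
- SICI: (0.054/0.35)/0.0468 = 3.30, n about 10.9

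Allowing for rounding in the inputs, these are close to the planned 10.

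**Step 5: the interim's back-reference.** None of sections 2.A to 2.E, or 3.A to 3.D2, describes an interim analysis. The reference in D3 has nothing to point to.

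**The case against.** The best defence is that this is loose wording in a safety section. The end of recruitment is stated three times as 10 completers, and C4, the analysis section, contains no stopping rule. On this view the dose-dependent wording is a slip for drug-related, and the sentence means only that the study ends whether the result is positive or null. If it is applied at 10 completers, it is harmless.

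That reading is possible, and it limits the severity. It does not rescue the sentence. If the first condition means any significant difference and the second means none, the two together cover every outcome. The sentence is then true whenever it is applied, and the missing time of application becomes the whole problem.

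A reader might go further and infer that the study was bound to stop at five subjects, because nothing could be significant there. The documents do not support this. It needs the second condition to mean nothing significant, although the wording points towards a literal reading that would almost never be met. It needs the sentence to apply at the N=5 look, whose stated purpose is re-estimation. It also needs the exact or continuity-corrected test, since the uncorrected approximation can reach 0.043. Finally, that look is triggered by enrolment, so there may be fewer than five complete pairs at that point.

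It is also fair to say that the undescribed re-estimation is a separate drafting gap. It is included here because it sits in the same paragraph and bears on the same planned N.

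**Conclusion.** The point holds as a minor inconsistency in the plan text. The first condition cannot be tested with one active dose at any N, and the only positive result the design can give satisfies neither condition. These two conclusions rest on the text alone. The second condition has no criterion, no rule for combining the three measures and no look, so it either almost never applies or leaves open an outcome-based stop short of 10 completers. The documents do not say which.

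The five-pair minimum of 0.0625 is an illustration that depends on assumptions D3 does not state, and it is not an estimate of what would have happened. A reader might also infer that the reported findings came from an early, data-driven stop. Section 8 gives no sign of one at five: its ICF p-value is unattainable with five pairs, and the approximate sample sizes are near 10. The reported results are not challenged.

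**What to change.** 1. Delete the conclusion sentence from D3. Leave the adverse-event and other safety text in D3 unchanged.
2. Add to C4, for example: *Recruitment ends when 10 subjects have completed both drug visits (visits 2 and 3). SICI, ICF and LICI are each compared between L-theanine and placebo once, on those 10 subjects.*
3. Delete the undescribed re-estimation at five enrolled from D3, so that D3 and the new C4 statement agree on a fixed 10 completers.

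The change is to wording only. The cost is that any early stop for efficacy or futility, and the sample-size re-estimation, are given up. The document already carries results, so the edit cannot alter how this study was run. It corrects the plan text and keeps the rule from being carried into the phase 2 study mentioned in the Background.

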5D. PHI is only needed for activities preparatory to research YES 🔀 NO	

6) DESCRIPTION OF PHI TO BE COLLECTED UNDER WAIVER

Name, age, sex, handedness, contact information, medical history, substance and nutraceutical use history. (Medical clearance documents to be requested from PCP will be obtained following signature on a separate CNE Authorization form)

7) ADVERTISEMENTS

The advertisement will be submitted as amendment if the protocol is approved.

8) RESRULTS INFORMATION

Primary results:

Compared to matching placebo, 400 mg single dose L-theanine elicited significantly higher post-pre drug change (Δ) of ICF (Mean±SE Δ ICF_{L-theanine}=0.073±0.073 vs. Δ ICF_{Placebo}=-0.341±0.176, p=0.016, Cohen's d = 1.02) and LICI (Mean±SE Δ LICI_{L-theanine}=0.145±0.100 vs. Δ LICI_{Placebo}=-0.068±0.053, p=0.037, Cohen's d = 0.91) within each individual. No significant difference was found for SICI (Δ SICI_{Placebo}= 0.005±0.060 vs. Δ SICI_{L-theanine}=0.059±0.028, p=0.450, Cohen's d = 0.35). L-theanine did not change unconditioned MEPs (or baseline rMT) differently than placebo (Table 1). No adverse effects from L-theanine were observed. The subjects were unable to guess the condition of drug (placebo vs L-theanine) after each session of experiment more accurately than random. (SE = standard error of the mean)
